**Veterans who are not on PrEP and who could benefit from PrEP (Objective set 2)**

For Veterans not on PrEP but who could benefit from it, baseline characteristics will be summarized at their first qualifying visit, while rates of HIV and STI testing/diagnoses within 12 months will be calculated using Poisson regression.

**Veterans using PrEP (Objective set 3)**

**Objective 3.1-** Baseline demographic and clinical characteristics will be described at the start of PrEP use during the study period, by regimen type (oral or CAB LA), using median and interquartile ranges or counts and proportions.

**Objective 3.2-** Proportions of CAB LA PrEP users initiating via oral lead-in or direct-to-injection will be reported.

**Objective 3.3 and 3.4-** PrEP adherence and usage patterns will be described using median and interquartile range for continuous data as well as absolute and relative frequencies for categorical data. Characteristics of individuals with and without delayed CAB LA injections as well as individuals with and without discontinuation will be compared using Pearson's chi-square tests for categorical variables and Mann-Whitney tests for continuous variables.

**Objective 3.5-** Incidence rates and confidence intervals for HIV testing, HIV diagnosis, STI testing/screening and STI diagnosis will be calculated using univariate Poisson regression. STI treatment prescription will be described using absolute and relative frequencies for categorical data.

**Objective 3.6-** For CAB LA PrEP users diagnosed with HIV, a timeline including details of oral PrEP prescriptions prior to CAB LA PrEP start, injections received, HIV tests performed, HIV treatment, viral load measurements, HIV drug resistance will be provided for each individual.

**3. AMENDMENTS AND UPDATES**

Amendment or update no	Date	Section of study protocol	Amendment or update	Reason
-	-	-	-	-

## 4. MILESTONES

**Table 1:** Study milestones

Milestone	Planned date
Final Protocol	19 December 2025
Tables Results	Q2 2027
Final Study Report	Q3 2027

## 5. RATIONALE AND BACKGROUND

HIV remains a persistent problem in the United States (US). In 2023, over 39,000 people were diagnosed with HIV in the US and 6 territories and freely associated states (US CDC, 2025). Over 80% were men, with 66% attributed to male-to-male sexual contact. Hispanic and Black individuals each accounted for more than a third. Ages 15-24 and 25-44 accounted for 18% and 60% of diagnoses, respectively. The South region represented 51% of new cases. The 2021 HIV/AIDS Strategy identified five priority populations disproportionately impacted by HIV: gay, bisexual, and other men who have sex with men (MSM), black women, transgender women, youth aged 13-24 years, people who inject drugs (White House, 2021).

Pre-exposure prophylaxis (PrEP), which consists in the use of antiretroviral medications by HIV-negative individuals with a substantial risk of contracting an HIV infection, is highly effective at preventing HIV when taken as indicated (Cancio-Suárez, 2023). As of August 2025, there are two daily oral medications for PrEP approved by the U.S. Food and Drug Administration (FDA). There are also two FDA-approved long-acting injectable forms of PrEP, one that is administered every other month and the other is administered twice yearly. Oral PrEP was introduced as a form of HIV prevention when the single tablet combination of tenofovir disoproxil fumarate (TDF) and emtricitabine (FTC) was approved by the FDA on July 16, 2012 (Roehr, BMJ 2012). The second oral PrEP option, a single tablet combination of tenofovir alafenamide (TAF) and FTC was approved on October 3, 2019 (The Lancet HIV, 2019).

Cabotegravir long-acting (CAB LA) is an injectable PrEP administered every two months for use in at-risk adults and adolescents and received FDA approval in December 2021 (US FDA, 2021). CAB LA may be initiated with optional short-term oral lead-in (OLI). Clinical trials have demonstrated the superior efficacy of CAB LA PrEP over daily oral TDF/FTC for HIV prevention (Durham, 2023). A second long-acting option for HIV prevention (Lenacapavir - LEN) was approved by the US FDA in June 2025 (Mullard, 2025). It is delivered in subcutaneous injections given every 6 months.

The US Centers for Disease Control and Prevention (CDC) recommend that people consider PrEP if they are HIV negative, have had anal or vaginal sex in the past six months, and have a sexual partner with HIV (especially if the partner has an unknown or detectable viral load), or

have not consistently used a condom, or have been diagnosed with a sexually transmitted infection (STI) in the past six months (US CDC, 2024). PrEP is also recommended to people who inject drugs and have an injection partner with HIV, or share needles, syringes, or other equipment to inject drugs. People who have been prescribed PEP (post-exposure prophylaxis) and report continued risk behavior or have used multiple courses of PEP may as well consider taking PrEP. People may also choose to take PrEP, even if these behaviors do not apply to them.

In 2022, of approximately 1.2 million people in the US who could benefit from PrEP, it was estimated that only around 36% had received a PrEP prescription (Fanfair, 2023). The Department of Veterans Affairs (VA) is the largest HIV care provider in the US; PrEP is a covered benefit for all enrolled Veterans (Huang, 2018). An analysis of 2014-2022 data of the Veterans Health Administration (VHA) showed an increase in the number of Veterans prescribed PrEP annually, from 361 in 2014 (5.6 per 100,000 Veterans in VHA care) to 6050 in 2022 (89.4 per 100,000) (Huang, 2025). While adherence to oral PrEP was high among Veterans in the period 2012-2016 (Huang, 2018), recent adherence data, including for long-acting injectable PrEP, are lacking. To be eligible for CAB-LA PrEP in the Veterans Health Administration, individuals must be at substantial risk of HIV acquisition (sex without condoms, recent or frequent sexually transmitted infections, sexual relationship with HIV infected partner, injection drug abuse with equipment sharing), prescribed cabotegravir by a provider experienced in PrEP, and meet at least one of the following additional criteria: intolerance to TDF/FTC or TAF/FTC, renal dysfunction, challenges with adherence to daily oral PrEP, or very high risk of HIV acquisition. Patients are excluded if they have significant noncompliance with follow-up or drug interactions with CAB (VA, 2022).

HIV testing is required to confirm that patients do not have HIV before starting PrEP (US CDC, 2025). People on daily oral PrEP need to see a health care provider every 3 months for repeat HIV tests, prescription refills, and follow-up. People using injectable PrEP need to see a healthcare provider every two or six months for an HIV test and the injections, depending on which option they chose (HIV.gov, 2025 a). Screening for other sexually transmissible infections (STIs) is an important part of PrEP clinical follow-up and monitoring (Jenness, 2017). It allows for early detection and treatment of STIs that would otherwise go undetected.

Understanding patterns of PrEP use is key to optimizing its effectiveness in HIV prevention and improve clinical practice and public health benefits. Analyzing how people use PrEP can help design effective strategies for uptake, adherence and continuation leading to better public health outcomes. This study will provide real-world evidence on PrEP use patterns, HIV testing and STI screening in individuals on either oral or LA PrEP, as well as potential incident HIV diagnoses on PrEP.

## **6. RESEARCH QUESTION AND OBJECTIVE(S)**

### **Objective set 1 -Veterans in care with no evidence of HIV infection at the beginning the calendar years under analysis**

- 1.1- Estimate the annual incidence proportion of HIV diagnoses among Veterans in care (actively enrolled in VHA care) without evidence of HIV infection at the beginning of

each calendar year under analysis

- 1.2- Among Veterans with an incident HIV diagnosis, characterize history of PrEP use.

**Objective set 2- Veterans in care with no evidence of HIV infection who are not on PrEP but could benefit from PrEP**

- 2.1- Describe the characteristics of Veterans in care who are not on PrEP but could benefit from PrEP
- 2.2- Estimate HIV testing and diagnoses rates, as well as rates of STI screening/testing rates, STI diagnoses among Veterans in care who are not on PrEP but could benefit from PrEP, over a 12-month period of follow-up

**Objective set 3- Veterans on care with no evidence of HIV infection who initiate PrEP (oral or CAB LA injectable) during the study period**

- 3.1- Describe the population of Veterans in care who initiated oral PrEP or CAB LA injectable PrEP, including their demographic, clinical and sexual behavioral characteristics, the year of PrEP initiation and the duration of follow-up
- 3.2- Describe the proportions of Veterans on care initiating CAB LA PrEP who used oral lead in (OLI) and proportion of those with direct to injection (DTI).
- 3.3- Describe adherence to oral and CAB LA injectable PrEP
- a) Oral PrEP use only: number days oral PrEP supplied divided by number of days in observational period
  - b) CAB LA injectable PrEP
    - Number of days covered by CAB LA PrEP divided by the number of days in the observation period
    - Timing and completion of initiation injections
    - Among complete initiators with at least one maintenance injection, timing of maintenance injections: all on time, any late injection (short delay not requiring reinitiation, long delay requiring reinitiation)
    - Baseline characteristics of users with all injections on time versus users with any late maintenance injection
- 3.4- Describe patterns of PrEP use
- a) Oral PrEP:
    - Discontinuation: any discontinuation, resumption of oral PrEP
    - Duration of oral PrEP use for the first period of use
  - b) CAB LA injectable PrEP
    - Discontinuation: any discontinuation, resumption of long-acting injections (with CAB LA injectable or LEN LA injectable) or oral PrEP after discontinuation
    - Oral bridging between discontinuation of CAB LA injections and resumption of CAB LA injections
    - Duration of CAB LA PrEP use in months

- first period of use
  - cumulative use throughout the study period in case of discontinuation followed by resumption of CAB LA PrEP injection(s)
  - Baseline characteristics of users discontinuing CAB LA PrEP versus users who did not discontinue
  - Proportion of CAB LA PrEP users with at least one maintenance injection who are on CAB LA PrEP at 12 months and 24 months after initiation and at the end of the study period
- 3.5- Described patterns of HIV and other STI testing/screening, diagnosis and STI treatment
- a) Assess the incidence of HIV testing and HIV diagnosis during the first period of PrEP use by PrEP modality
  - b) Estimate the frequency of testing for STI diagnosis and STI diagnosis by PrEP modality
    - in the 6 months preceding PrEP initiation
    - during the first period of PrEP use
  - c) Describe the proportion of diagnosed STI with a relevant antimicrobial prescription
- 3.6- Among CAB LA PrEP users diagnosed with HIV (during CAB LA PrEP use or after CAB LA PrEP discontinuation)
- a) Describe the timing of incident HIV diagnoses relative to timing of CAB LA PrEP usage and testing for HIV
  - b) Describe adherence to PrEP injection schedule, HIV treatment, virologic suppression, concomitant STI diagnosis, and HIV drug resistance

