### **Research Question and Objective(s)**

**Objective set 1 -Veterans in care with no evidence of HIV infection at the beginning of the calendar years under analysis**

- 1.1- Estimate the annual incidence proportion of HIV diagnoses among Veterans in care without evidence of HIV infection at the beginning of each calendar year under analysis
- 1.2- Among Veterans with an incident HIV diagnosis, characterize history of PrEP use.

**Objective set 2- Veterans in care with no evidence of HIV infection who are not on PrEP but could benefit from PrEP** (*refer to protocol section 7.2.1 for inclusion criteria*)

- 2.1- Describe the characteristics of Veterans in care who are not on PrEP but could benefit from PrEP
- 2.2- Estimate HIV testing and diagnoses rates, as well as rates of STI screening/testing rates, STI diagnoses among Veterans in care who are not on PrEP but could benefit from PrEP, over a 12-month period of follow-up

**Objective set 3- Veterans in care with no evidence of HIV infection who initiate PrEP (oral or CAB LA injectable) during the study eligibility period for PrEP initiation**

- 3.1- Describe the population of Veterans in care who initiated oral PrEP or CAB LA injectable PrEP, including their demographic and clinical characteristics, the year of PrEP initiation and the duration of follow-up
- 3.2- Describe the proportions of Veterans in care initiating CAB LA PrEP who used oral lead in (OLI) and proportion of those with direct to injection (DTI).
- 3.3- Describe adherence to oral and CAB LA injectable PrEP
  - a) Oral PrEP use only: number days oral PrEP supplied divided by number of days in the observation period
  - b) CAB LA injectable PrEP
    - Number of days covered by CAB LA PrEP divided by the number of days in the observation period
    - Timing and completion of initiation injections

- Among complete initiators with at least one maintenance injection, timing of maintenance injections: all on time, any late injection (short delay not requiring reinitiation, long delay requiring reinitiation)
  - Baseline characteristics of users with all injections on time versus users with any late maintenance injection
- 3.4- Describe patterns of PrEP use
- a) Oral PrEP:
    - Discontinuation: any discontinuation, resumption of oral PrEP
    - Duration of oral PrEP use for the first period of use
  - b) CAB LA injectable PrEP

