**a) Oral PrEP coverage in the 12 months following initiation**

PrEP dispensing is considered as a proxy for PrEP use. The number of dispensing events will be described.

The number of pills dispensed/days covered per dispensing event will be calculated.

Proportion of days of access to oral PrEP in the 12 months following index PrEP initiation

Follow-up (FU) will be censored at first of:

- 12 months after index date
- Loss to follow-up
- Death
- Study end

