**b) Adherence to CAB LA PrEP schedule**

- Proportion of days covered by CAB LA PrEP in the 12 months following initiation: number of days covered by CAB LA PrEP divided by the number of days in the observation period

Follow-up will be censored at first of:

- a) 12 months after index date
- b) Loss to follow-up
- c) Death
- d) Study end

Coverage by LA PrEP will be determined based on the duration of days covered by the medication, according to the label.

- 1st injection: coverage = 37 days (30 days of coverage + 7-day injection window)
- Subsequent injections: coverage = 67 days (60 days of coverage + 7-day injection window)

Each calendar day will only be counted once, even if there is an overlap between coverage from the prior injection and date of the next injection.

- **Complete versus incomplete initiation:**

- Among all Veterans with  $\geq 1$  CAB LA injection:

→ Complete initiation (2nd injection received within 67 days following the 1st injection)

- 2nd initiation injection on time: 2nd injection between 23 and 37 days following the first injection
- 2nd initiation injection late: 2nd injection between 38 and 67 days following the first injection

→ Incomplete initiation: >67 days without injection following the first injection

- Among incomplete initiators

Any additional injection(s) >67 days after the 1st injection (Yes/no)

If yes:

- o Timing of the 1st additional injection after the last injection of the “incomplete initiation” (interval in days, number with interval of 68-97 days and interval >97 days)
- o Complete versus incomplete reinitiation
- o Interval between the first two reinitiation injections ( $\leq 37$ ; 38-67, 68-97, 98-127;  $\geq 128$  days apart)

• **Timing of CAB LA PrEP maintenance injections:** among complete initiators with at least one maintenance injection

Determined based on the time between initiation injections (Table 3)

- Total number of maintenance injections per individual
- All on time
- Any late maintenance injection (short delays not requiring reinitiation, long delays requiring reinitiation): number of short and long delays, number of individuals with 1, 2, 3 or more short delays, number of individuals with 1, 2, 3 or more long delays, median duration of short and of long delays

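### The oral adherence formula in objective 3.3 a) is an uncapped possession ratio and contradicts the proportion-of-days measure used elsewhere in the protocol

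*Protocol*

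**What the plan says.** **Oral PrEP, formula.** Section 6, objective 3.3 a), gives "Oral PrEP use only: number days oral PrEP supplied divided by number of days in observational period", and the synopsis gives the same ratio. It is the only oral adherence formula in the protocol.

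**Oral PrEP, outcome.** Section 7.3.3 a) names the outcome "Proportion of days of access to oral PrEP in the 12 months following index PrEP initiation". The building block is per fill: "The number of pills dispensed/days covered per dispensing event will be calculated". Nothing is said about overlapping fills or about supply that runs past the end of the window.

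**Labels elsewhere.** Table 2 (Section 7.1) gives one set of censoring criteria for objective set 3, oral and CAB LA together, and calls the measure a proportion of days covered. Section 7.7.1.1 (objectives 3.3 and 3.4) reports both modalities in one sentence as the percentage of days with access over the first 12 months.

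**CAB LA.** Section 7.3.3 b) uses "number of days covered by CAB LA PrEP divided by the number of days in the observation period" and adds "Each calendar day will only be counted once, even if there is an overlap between coverage from the prior injection". The credit per injection includes a 7-day window: "coverage = 37 days (30 days of coverage + 7-day injection window") for the first and "coverage = 67 days (60 days of coverage + 7-day injection window") for each later one.

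**The concern.** Days supplied over days observed adds up everything dispensed in the window, whether or not the tablets could be taken within it. A late fill can therefore offset an earlier period without drug, and the ratio can pass 100%. A proportion of days with access can do neither. The protocol thus states one formula twice and describes a different quantity in three other places. Two programmers, one working from Section 6 and the other from Section 7.3.3, would get different results from the same dispensing records.

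Adherence is a named objective, and Section 5 says that recent adherence data, including for injectable PrEP, are lacking. The oral level is therefore a result that readers will use, and it will stand beside a CAB LA figure that is capped by its definition.

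**Working it through.** **Inputs.** The window is 12 months, taken as 365 days without earlier censoring. The protocol does not state a fill length, so 30, 60 and 90 days are assumptions. Section 5 describes three-monthly visits for refills on daily oral PrEP, which makes 90 days plausible.

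**The plan's own figures.** CAB LA credit is 30 + 7 = 37 days and 60 + 7 = 67 days. Both reproduce.

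**Two oral measures.**
- Possession ratio (as written) = total days supplied by fills in the window / days observed.
- Proportion of days covered = unique days in the window with drug on hand / days observed, with overlapping supply moved forward.

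With overlap moved forward, the numerators differ by exactly the supply still unused when the window closes. The first measure can therefore never be below the second.

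**1. Exceeding 100%.** Every fill is exactly on time, so true coverage is 365/365 = 100%.
- 30-day fills, days 0 to 360: 13 × 30 = 390; 390/365 = 106.8%.
- 60-day fills, days 0 to 360: 7 × 60 = 420; 420/365 = 115.1%.
- 90-day fills on days 0, 90, 180, 270 and 360: 5 × 90 = 450; 450/365 = 123.3%.

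No early refilling is needed. In the last case the day-360 fill has 5 days inside the window and 85 outside, and 450 − 85 = 365.

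**2. Masking a gap.** 90-day fills on days 0, 80, 160 and 355.
- As written: 4 × 90 = 360; 360/365 = 98.6%.
- Days covered: the first three fills, with overlap carried forward, cover days 0 to 269 (270 days). The fourth covers days 355 to 364 (10 days). 280/365 = 76.7%.
- Days 270 to 354, 85 days without drug, do not show in the 98.6%. The difference, 360 − 280 = 80 days, is the part of the last fill that lies beyond the window.

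The carry-forward rule itself matters. Without it, the first three fills cover only days 0 to 249, and the result is (250 + 10)/365 = 71.2%.

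**3. The 7-day window in CAB LA coverage.**
- Every injection on the last day of its window (days 0, 37, 104, 171, 238, 305): 365/365 = 100% with 37/67 days, and (30 + 5 × 60)/365 = 330/365 = 90.4% with 30/60 days.
- Injections at nominal times, then stopping: the window adds 7 days once, 7/365 = 1.9 points, because earlier windows overlap the next injection.

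**4. Oral PrEP with every refill 7 days late.**

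| Fill length | As written | Unique days covered |
|---|---|---|
| 30 days (10 fills) | 300/365 = 82.2% | 82.2% |
| 60 days (6 fills) | 360/365 = 98.6% | 330/365 = 90.4% |
| 90 days (4 fills) | 360/365 = 98.6% | 344/365 = 94.2% |

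**The case against.** **The objective line is only shorthand.** On this view the methods sections govern. They describe a bounded day count, and rules for overlap and truncation usually belong in the SAP. If that is the intention, the results above 100% and the masked gaps do not arise. But the synopsis and Section 6 then carry a wrong formula. It is a stated rule, not an omitted detail, and it is the only one for oral PrEP, so it still has to be corrected.

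**Gaps are reported elsewhere.** Section 7.3.3 reports oral discontinuation at 30 and 90 days after the previous dispensing. In the gap example, the 195 days between days 160 and 355 exceed both limits. This is true and limits the harm, but it does not correct the adherence figure itself.

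**A stronger reading is tempting.** A reader might infer that the 7-day window inflates CAB LA adherence and leaves neither figure interpretable. The documents do not support that:
- The window is an explicit choice that Section 7.3.3 ties to the label. It matches the protocol's on-time limits (23–37 days for the second injection, 53–67 days in Table 3).
- It adds materially only when injections are repeatedly late.
- A wide contrast for equal lateness (CAB LA 100%, oral 82.2%) depends on assuming 30-day fills. With 90-day fills the stated oral formula gives 98.6%.
- Observation periods already match: Section 7.3.3 lists the same four censoring events for both modalities.
- No oral versus CAB LA adherence test is planned. Section 7.7 calls the analyses descriptive, and Section 7.9 already says that dispensing is a proxy for use.

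**Conclusion.** The oral formula in objective 3.3 a) is wrong as written. It contradicts Table 2, Section 7.3.3 and Section 7.7.1.1, and it differs in kind from the CAB LA measure. The error is upward by the supply left when the window closes: 23 points for on-time 90-day fills (123.3% against 100%) and 22 points in the gap example (98.6% against 76.7%). Those sizes rest on an assumed 90-day fill and a full 365-day window. With on-time 30-day fills the excess is 6.8 points. They show what the formula allows for single patients and do not predict the cohort median, which depends on fill lengths and refill timing that the protocol does not give.

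The 7-day CAB LA window is not an error. It is a difference in definition to be disclosed, worth up to 9.6 points (100 − 90.4) in the extreme case and about 1.9 points for nominal timing followed by stopping.

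**What to change.** In the synopsis and in Section 6, restate objective 3.3 a) as unique days covered by dispensed oral PrEP divided by days in the observation period. Overlapping supply is carried forward, each calendar day is counted once, supply is cut at the end of the window, and the maximum is 100%. This matches the labels in Table 2, Section 7.3.3 and Section 7.7.1.1 and the counting rule already set for CAB LA. The denominator needs no change.

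In the report, note that CAB LA coverage includes a 7-day window and that oral coverage has no such allowance. A sensitivity row for CAB LA at the protocol's own 30 and 60 days is optional.

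The cost is one sentence in two places and a note in the report, with no new data. The downside is that oral adherence will look lower than under the stated formula.
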